#### **Standard of Care (SOC) Arm**

Subjects randomized to SOC arm are provided with the appropriate standard of care depending upon their risk level (as determined by their individual provider or AHWFB Maternal-Fetal Medicine provider)

- High-risk women:
  - Scheduled in-person visit 1 week postpartum with their OB
  - Scheduled in-person visit 4-6 weeks postpartum with their OB
  - Additional visits as clinically indicated determined by the patient's provider(s).
  - Patients with high blood pressure may be instructed to check home blood pressures at the discretion of their primary provider
  - Blood pressure cuffs are not routinely provided by primary provider
- Low-risk women:
  - Typically scheduled in-person visit 4-6 weeks postpartum with their OB
  - Additional visits at patient/provider discretion

The individual subject's provider will perform all follow-up postpartum OB visits. The study team will not initiate the scheduling of any follow-up postpartum OB visits for either study arm (this is the responsibility of the individual subject). However, the study team members may encourage subjects to make and keep their 4-6 week postpartum visit. All physician/health care provider visits will be at the expense of the individual subject.

### **Remote Blood Pressure Monitoring (rBPM) Arm**

Subjects randomized to rBPM arm receive the appropriate standard of care depending upon their risk level, as well as the remote BP monitoring app (BabyScripts) and Bluetooth enabled BP cuff/monitor, and will receive the following equipment and monitoring:

- High-risk women:
  - Scheduled in-person visit 1 week postpartum with their OB
  - Scheduled in-person visit 4-6 weeks postpartum with their OB
  - Additional visits as clinically indicated determined by the patient's provider(s).
- Low-risk women:
  - Typically scheduled in-person visit 4-6 weeks postpartum with their OB
  - Additional visits at patient/provider discretion
- Provided with a specialized, Bluetooth enabled BP monitoring cuff (Clinically Validated, A&D Medical Wireless Blood Pressure Monitor-Upper Arm (*Appendix 2*)
  - The standard BP cuff is designed to fit a wide-range of arm circumferences (8.6-16.5 inches) and can accommodate an individual with a BMI up to 45-50 kg/m^2.
  - An extra-large BP cuff will be available for women with larger arm circumferences (16.5-23.6 inches), or BMI >50 kg/m^2. The extra-large BP cuff is not Bluetooth enabled and the subject will need to manually enter BP data from the BP monitor into the BabyScripts app. We expect that this extra-large BP cuff will be needed for <10% of our subjects (based on historical data from other facilities utilizing BabyScripts app)
- Assistance with downloading BP monitoring smart phone app, BabyScripts™ (*Appendix 3a and 3b*)
- Verbal and written instructions, to conduct BP checks at home (with reminder notifications sent via the BabyScripts app): (*Appendix 4*)
  - Twice daily on days #1 through #16 (day #1 = day after hospital discharge)
  - At least once daily on days #17 through # 21
  - Due to the customization limitations of the Babyscripts app, subjects will receive twice daily reminder notifications for the duration of the study enrollment period (21 days); however, the NEST coordinators will remind the subjects that we are only asking them to check their BP once daily on days #17 through #21.
- Subjects will be asked to demonstrate the accurate use of the BP cuff/monitor and the BabyScripts app for a study team member, prior to being discharged from the hospital. This is to evaluate their level of understanding, to confirm the BP cuff is the correct size, and that the equipment is working properly.
- All BP measures and any alerts will be sent in real-time to a secure cloud-based portal, DIANA. This portal will be accessible only to designated staff members. Clinically-relevant readings and symptoms initiate an alert to BabyScripts call center and then are communicated directly to AHWFB Maternal-Fetal Medicine staff
- AHWFB Maternal-Fetal Medicine on-call staff are available for response 24/7/365
- Acceptability and user experience data will be collected via on-line REDCap survey between 21-28 days after enrollment (*Appendix 5a and 5b*)

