After obtaining electronic consent via REDCap, the subject will be asked to complete a baseline demographic questionnaire (*Appendix 1a and 1b*). After this brief questionnaire is completed, the subject will then be randomized into one of two study arms; either rBPM or SOC. Study ID numbers will be assigned to each subject. Randomization assignment will be completed by a study staff member using the REDCap randomization tool after enrollment and after the subject has completed the baseline questionnaire in REDCap or in real time if the subject is enrolled in the hospital after delivery. All subjects have an equal chance of being assigned to either the rBPM or SOC study arm. The study arm assignment will be documented in the subject's EMR. The subjects that were enrolled during a prenatal clinic visit will not be aware of their study arm assignment until after they have delivered their infant(s) at The Birth Center. Logistically, it is not feasible to complete the randomization in real-time in the outpatient setting, and there are no study activities that occur between the time of the subject's outpatient prenatal clinic visit and their delivery at The Birth Center.

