#### **If BP critically elevated ( $\geq 160/110$ )**

- Alert is generated through the BabyScripts app for either diastolic alone or systolic alone readings or if both readings are above the threshold

- Subject receives an immediate text and email message via BabyScripts letting subject know they have a critically elevated BP reading and asking the subject to complete a symptom checklist directly in the app. If they have no symptoms, the “no symptoms” icon must be checked in the app.
- On-call MFM staff is alerted by BabyScripts call center within 60 minutes [14-19].
- Provider (or nurse – see 2nd bullet below) calls subject for further evaluation and instructions within 45 minutes:
  - If this is new onset hypertension irrespective of symptoms, the subject is referred to OB triage and instructed to present without delay.
  - If subject also has a chronic or known history of high BP, but no other symptoms, then a RN reviews the BP measurements, discusses with the clinic or on-call MFM physician, and contacts the subject with the provider’s recommended instructions.

For the subjects in the rBPM study arm, acceptability and user experience data will be collected via on-line REDCap questionnaire ~ 21 – 28 days after study enrollment, or within one week of the subject’s completion of the study. A unique link to the REDCap questionnaire will be sent via email to the subject. If the questionnaire is not completed within 1 week of being sent, a reminder email to complete the survey will be sent weekly for a maximum of 3 weeks. Completion of this on-line survey is expected to take <= 5 minutes.

Per standard of care, the rBPM study arm subject’s initial postpartum OB provider visit will be scheduled either at ~1 week after delivery for high risk subjects and at ~4-6 weeks after delivery for subjects with a low risk of postpartum complications. Additional follow-up medical care visits may be scheduled at the discretion of the provider and the subject. All follow-up medical care, regardless of the study arm, will be at the expense of the individual subject.

The subjects randomized to the experimental study arm will be provided with a specialized BP cuff/monitor at no cost. The subject will be able to keep the BP cuff/monitor for personal use after they have completed the study. The subject does not need to return the monitor.

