#### Secondary:

A high proportion (>90%) of patients indicating satisfaction with use of the remote BPM tool, with no significant difference in satisfaction according to patient insurance status. Satisfaction to be assessed at 3-4 weeks postpartum through a unique link to a satisfaction survey sent to participant.

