## **Analytical Plan**

The subject will complete a baseline demographic questionnaire at the time of enrollment. This questionnaire will be completed electronically through a unique link via REDCap. Additionally, subjects in the rBPM study arm will be asked to complete a post-study questionnaire electronically through a unique link via REDCap ~ 1 week after subject has completed the study.

The following EHR-based clinical measures will be obtained from each subject:

- Demographics
- History of hypertension or use of blood pressure lowering agents
- Pregnancy-related data (e.g. blood pressure, pre-pregnancy BMI, weight gain, complications, pre-pregnancy diabetes, gestational diabetes, delivery complications)
- Birth outcomes, including gestational age at delivery, cesarean or vaginal delivery, singleton or multiparous delivery, birth weight
- Length of stay of admission and any readmissions through 12 weeks postpartum
- Use of blood pressure lowering agents through 12 weeks postpartum

We will link EHR, BP, baseline demographic questionnaire data, billing, and user satisfaction data to inform study questions as described above. Data will be reviewed for missingness, with multiple imputation performed as appropriate. Initially, data will be analyzed using descriptive statistics. Comparison between groups may be performed using chi square tests for proportions, and t-tests or ANOVA procedures for continuous variables. Crude and adjusted regression analysis will be performed to identify independent outcome predictors. Other inferential statistical analysis will be conducted as appropriate.

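### The satisfaction survey has conflicting time anchors, one of which can fall before delivery, and its equity criterion by insurance is a non-significant test that fewer replies make easier to pass

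*Combined protocol and SAP*

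**What the plan says.** Four places in the Combined protocol and SAP time the same survey:

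- Remote Blood Pressure Monitoring (rBPM) Arm: "Acceptability and user experience data will be collected via on-line REDCap survey between 21-28 days after enrollment".
- The questionnaire paragraph at the end of the section on critically elevated BP: about 21-28 "days after study enrollment, or within one week of the" subject's completion of the study. Weekly reminders follow for at most 3 weeks.
- Feasibility and acceptability outcomes, Secondary: "Satisfaction to be assessed at 3-4 weeks postpartum through a unique link to a satisfaction survey sent to participant".
- Analytical Plan: rBPM subjects "will be asked to complete a post-study questionnaire electronically through a unique link via REDCap ~ 1 week after subject has completed the study".

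Methods and Measures allows enrollment at a prenatal visit from 24 weeks' gestation as well as after delivery, and states: "The subjects that were enrolled during a prenatal clinic visit will not be aware of their study arm assignment until after they have delivered". Interventions and Interactions has the cuff handed over in hospital after delivery. Monitoring Day 1 is the day after discharge, and monitoring ends on Day 21.

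The secondary feasibility outcome is satisfaction above 90%, "with no significant difference in satisfaction according to patient insurance status". No margin, significance level or expected response rate is given for it. For proportions, the Analytical Plan names chi-square tests.

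**The concern.** Two separate weaknesses affect one outcome.

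The first is timing. A woman surveyed before delivery has no device to rate, so her answer does not measure satisfaction with remote monitoring. Only the rBPM arm is surveyed, so receiving the link would also tell her which arm she is in. Staff who build the REDCap trigger from the arm description would naturally use the consent date.

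The second is the equity criterion. Failing to reject equality does not show that Medicaid or uninsured women and privately insured women are similarly satisfied. The fewer women reply, the more likely the criterion is to be met, so poor data collection favours the hoped-for conclusion. Performance within socioeconomic subgroups is a stated comparison of the trial, so a claim of no gap would carry weight.

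**Working it through.** **Timing.** Inputs: enrollment from 24 weeks; survey 21-28 days later; monitoring to Day 21 after discharge (all from the protocol). Delivery at 39 weeks is my assumption.

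1. Earliest enrollee: 24 + 3 to 24 + 4 = 27-28 weeks. Delivery is (39 − 24) × 7 = 105 days after enrollment, so the survey goes out 105 − 28 = 77 to 105 − 21 = 84 days before it.
2. If discharge is *d* days after enrollment, Day 21 falls *d* + 21 days after enrollment. It is reached by day 28 only if *d* ≤ 7.
3. With delivery at 39 weeks, the survey precedes delivery for anyone enrolled before 35-36 weeks. The share depends on gestational age at enrollment, which is not given. If enrollment is uniform over the stated range, the share is:

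| Enrollment range (weeks) | Surveyed before delivery |
|---|---|
| 24-32 | 100% |
| 24-39 | 73-80% |
| 32-39 | 43-57% |
| 34-39 | 20-40% |
| 36-39 | 0% |

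4. The postpartum anchors also differ somewhat. Within one week of completion means Day 22-28 after discharge, and about one week after completion means about Day 28. If discharge is *L* days after delivery, 3-4 weeks postpartum is Day 21 − *L* to Day 28 − *L*. That window opens before monitoring ends but closes after it whenever *L* is under 7.

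**Equity criterion.** The plan has no figure of its own to reproduce. Inputs: 1000 women in the rBPM arm (Sample Size); a 2:1 split of Medicaid/uninsured to private, assumed from the nearly two-thirds in the Background. Also assumed: two-sided 0.05, true satisfaction of 87% versus 95%, and the response rates.

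Chance of a non-significant result = 1 − Φ[(d − 1.96·SE0)/SE1], where d = 0.08, SE0 is the pooled and SE1 the unpooled standard error.

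Full response, 667 and 333 women: pooled proportion 0.897, SE0 = 0.0204, SE1 = 0.0177. Then (0.08 − 1.96 × 0.0204)/0.0177 = 2.26, so the chance is 1.2%.

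The last column applies another rule to the same gap: the 95% CI must lie within ±15 points, the figure the plan uses for adherence. At full response its formula is Φ[(0.15 − 0.08)/0.0177 − 1.96] = Φ(1.99), about 98%.

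| Response | Replies | Non-significant, formula | Non-significant, simulation | Passes 15-point rule, simulation |
|---|---|---|---|---|
| 100% | 667 + 333 | 1% | 1% | 98% |
| 50% | 333 + 167 | 17% | 16% | 81% |
| 30% | 200 + 100 | 41% | 41% | 59% |
| 20% | 133 + 67 | 59% | 56% | 44% |

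Other gaps, simulated at 100%, 50%, 30% and 20% response: for 85% versus 95%, non-significance occurs in 0.1%, 5%, 23% and 40%; for 90% versus 95%, in 20%, 51%, 71% and 79%.

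**What a margin rule does.** For illustration, take a 10-point margin, true satisfaction of 90% in both groups and one-sided 0.025. The chance of showing similarity is 99.9%, 94%, 78% and 60% at the same response rates, so low response now makes the claim harder. Replies needed for 80% power are 318 at 10 points and 1272 at 5 points; the latter exceeds the arm.

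**The case against.** The strongest reply is that the enrollment wording is loose, not operative. The outcome definition is postpartum, the Analytical Plan calls the survey post-study, and the questionnaire paragraph offers completion as an alternative. The arm section itself describes the 21 monitoring days as an enrollment period, and on that reading 21-28 days roughly agrees with the other anchors. Methods and Measures also says that nothing study-related happens between the prenatal visit and delivery. This stands as far as it goes: the documents do not establish that surveys would go out before delivery. It does not remove the contradiction. The same protocol speaks of women enrolled at prenatal visits and places the baseline questionnaire at enrollment, so the literal reading is an ordinary one.

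A reader might infer that most prenatal enrollees would be surveyed too early. The documents give no distribution of gestational age at enrollment, and the share runs from 0% to 100% across the ranges tried.

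On equity, the low response rates are mine. The plan has reminders and provides for multiple imputation as appropriate, and at full response a 10-point gap would almost surely be detected. That limits the harm but does not make non-significance evidence of similarity; a 5-point gap (90% versus 95%) passes about 20% of the time even at full response.

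A reader might also reach for the plan's 10- and 15-point figures as ready-made margins. They are set for smartphone/app access and for adherence, not satisfaction. The 15-point figure would accept the 8-point gap more often than the present rule at every response rate shown except 20%.

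**Conclusion.** The point holds as an unreconciled contradiction in the survey's anchor and, separately, as a badly framed equity criterion. Followed literally, the enrollment rule surveys some rBPM women before they have used the device and discloses their arm; how many cannot be computed. It would go too far to call the satisfaction data meaningless or the arm unmasked as an expected result, because the other passages point to postpartum timing.

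For the equity criterion, the chance of missing an assumed 8-point gap rises from about 1% at full response to 56% at 20%. This rests on the assumed 87% and 95%, the 2:1 split, two-sided 0.05 and the assumed response rates.

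Satisfaction is a secondary outcome measured in one arm. Neither weakness affects the randomised comparison or the primary clinical and cost outcomes. The correction is worth making because it is cheap, but it is not a must-fix for the trial's main conclusions.

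**What to change.** 1. Use one anchor in all four places (the rBPM arm section, the questionnaire paragraph, the secondary feasibility outcome and the Analytical Plan): delivery discharge, after monitoring ends on Day 21, for example Day 22-28 after discharge.
2. Replace the non-significance criterion with the estimated difference in satisfaction, Medicaid/uninsured minus private, and its 95% CI. Judge it against a satisfaction margin that the sponsor prespecifies and justifies, and do not carry over the adherence margin.
3. Report survey response rates by insurance group.

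The cost is a changed REDCap trigger date and revised wording; nothing in the intervention changes. The downside is that with low response, or with a tight margin, the equity claim may not be provable. The report would then give the interval and say so.

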### **Subjects selection criteria**

### **Inclusion Criteria**

- Women that received prenatal care at one of the AHWFB OB/MFM outpatient clinic locations (Downtown Health Plaza, Clemmons Plaza, and Shepherd Street)
- Women that delivered an infant(s) at The Birth Center at AHWFB
- Women that delivered an infant(s) at home or outside facility, and were transported to AHWFB and received postpartum care in The Birth Center
- Currently resides in Forsyth County, NC
- 18 years of age or older
- Able to read and understand either English or Spanish
- Owns or has daily access to a smartphone (iOS or Android operating system) and Wi-Fi or monthly mobile data plan

### **Exclusion Criteria**

- Women that delivered an infant(s) at any location other than The Birth Center at AHWFB
- Women that did not receive postpartum care at The Birth Center at AHWFB
- Resides outside of Forsyth County, NC
- Under 18 years of age
- Unable to read or understand either English or Spanish
- Does not own or have daily access to a smartphone (iOS or Android operating system)
- Owns a smartphone but does not have Wi-Fi or monthly mobile data plan

### **Sample Size**

It is estimated that approximately 5,000 women will deliver in Forsyth County over a 30 month time period. Of these, we anticipate that approximately 2000 women will be randomized equally (1000 in each study arm) during this time period.

### **Interventions and Interactions**

After obtaining informed consent electronically via REDCap, all subjects will be asked to complete a questionnaire using REDCap in order to collect baseline demographic data. Collecting this demographic data directly from the subject is to ensure accuracy. It has been reported that race, ethnicity, and even preferred language data may be missing from a subject's EMR or may have been previously entered into the EMR incorrectly (internal report). Additionally, collecting data on the subject's education level and marital status may help inform health disparities among various subject groups.

The subject will be directed to the demographic questionnaire after signing the electronic consent form via REDCap. The questionnaire must be completed in order to randomize the subject to a study arm. It is estimated that it will take  $\leq 5$  minutes to complete the baseline questionnaire. The baseline questionnaire will be available in both English and Spanish.

The subjects randomized to the rBPM study arm will receive a specialized Bluetooth enabled BP cuff/monitor from a NEST Coordinator in the hospital after delivery and before they are discharged home. The subject will receive both verbal and written education (in the subject's primary language) on the correct use of the specialized BP cuff/monitor. (*Appendix 7a and 7b*). The BabyScripts app will be downloaded on the subject's personal smartphone utilizing either an iOS or Android operating system. Instructions on the use of the BabyScripts app will be provided verbally and in writing (in the subject's primary language). The data entered into the BabyScripts app by the subject includes the following: name, email, DOB, cell phone number, pre-pregnancy weight, height, and date of (actual or expected) hospital discharge following delivery. The subject's pre-pregnancy weight and height are utilized by the app to calculate the subject's BMI, which will then help to identify the correct size of BP cuff that the

subject should be using for this study. Using an oversized or undersized BP cuff can result in erroneous BP measurements. The BabyScripts app is downloaded at no cost to the subject. Per the Master Agreement with BabyScripts, BabyScripts does not sell or share any personal data collected through the app.

The subject's education/training for participating in this research study is expected to take approximately 10 - 15 minutes, but the amount of time needed may vary based on the individual subject's level of understanding. After completing the training, a NEST Coordinator must observe a successful subject-directed trial of the rBPM equipment and app. The NEST Coordinator will document any identified barriers that may limit the subject's successful participation in the study.

The subject will use the specialized BP cuff/monitor to measure their BP twice-daily beginning on the morning of the day following hospital discharge. This day will be noted as "Day 1". Twice daily BP monitoring will continue through Day 16. Then, starting on Day 17, the subject will need to obtain their blood pressure only once daily in the morning, and continuing daily through Day 21. Subject's BP measurements will no longer be transmitted via BabyScripts app beginning on Day 22. The subject will receive a reminder text via the BabyScripts app when it is time to obtain their BP. Due to the limitations for customization, the Babyscripts reminder notifications will be sent twice daily (one in the morning and once in the evening) for the entire 21 day study period. . It is expected that it will take the subject less than 5 minutes (after a 5-10 minute rest period that is recommended to for the most accurate reading) to obtain each BP measurement. The subject's BP measurements, and any alerts are sent in real-time to a secure cloud-based portal. If the subject's BP falls within the normal range ( $\leq 140/90$ ), they will receive notification via the BabyScripts app, that their BP reading is normal. Any clinically relevant BP readings (defined below) will initiate an alert to the BabyScripts call center staff, who then communicates directly with a member of AHWFB Maternal-Fetal Medicine (MFM) staff. An assigned (or on-call) MFM staff member is available for response 24/7/365. While BabyScripts acts in real-time to alert the provider, any issues with wait time, unanswered phone lines, etc. may lead to delays to when the subject can expect to hear from the provider. Alert calls received from BabyScripts are documented in the subject's EMR.

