#### **If BP mildly elevated ( $\geq 140/90$ )**

- Alert is generated through the BabyScripts app for both or either diastolic alone or systolic alone readings above the threshold
- Subject receives an immediate text and an email message via BabyScripts letting the subject know they have a mildly elevated BP reading and asking the subject to complete a symptom checklist (headache, vision changes, severe abdominal pain, swelling of hands and face, shortness of breath/anxiety) directly in the app. If they have no symptoms, the "no symptoms" icon must be checked in the app. (*Appendix 8a and 8b*)
- Subject is instructed via BabyScripts app to recheck BP in 10 minutes
- The MFM staff member or provider is alerted by the BabyScripts call center within 4 hours
- MFM staff member or provider calls subject for further evaluation and instructions:
  - If this is new onset and subject has no symptoms, then subject will be scheduled for an office visit in 1-3 days.
  - If has chronic or known history of hypertension and subject has no symptoms, then they will continue monitoring BP per study protocol.
  - If subject has symptoms, she will be referred to OB triage

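### A reading of exactly 140 systolic or 90 diastolic is both normal and an alert under the protocol's stated cut-offs

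*Combined protocol and SAP*

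**What the plan says.** Three places in the combined protocol and SAP set BP cut-offs for women in the remote-monitoring arm.

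- **Interventions and Interactions**, normal message: if a woman's BP "falls within the normal range ( $\leq 140/90$ ), they will receive notification via the BabyScripts app" and be told the reading is normal. The boundary is included. The following sentence reads "Any clinically relevant BP readings (defined below) will initiate an alert to the BabyScripts call center staff", so the alert definition is to be found in the two subsections that come next.
- **Mild elevation subsection**: the heading is "If BP mildly elevated ( $\geq 140/90", with the boundary included again. Its first bullet generates the alert "for both or either diastolic alone or systolic alone readings above the threshold". The woman is told that the reading is mildly elevated. She is asked to complete a symptom checklist and to recheck in 10 minutes, and the call center alerts MFM staff within 4 hours. For one group the next step is: "If this is new onset and subject has no symptoms, then subject will be scheduled for an office visit in 1-3 days".
- **Critical elevation subsection**: the heading is "If BP critically elevated ( $\geq 160/110" and the first bullet alerts "for either diastolic alone or systolic alone readings or if both readings are above the threshold". MFM staff are alerted within 60 minutes, and new-onset cases go to OB triage whether or not they have symptoms.

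No section states which cut the app applies to a reading exactly at a threshold.

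**The concern.** The normal range and the alert range should not overlap, and together they should cover every reading. Here both include the value 140 and the value 90. A woman at home with such a reading could receive a normal message and a mildly elevated message for the same measurement.

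The alert bullets add a second ambiguity. They speak of readings above the threshold, while their own headings say at or above it. Taken strictly, the mild-elevation bullet agrees with the normal range and contradicts its heading. The woman then gets the normal message only and none of the mild-elevation follow-up.

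These two consequences are alternatives: contradictory messages on one reading of the text, a missed alert on the other. Either is undesirable in a trial whose rationale is missed or delayed diagnosis of postpartum hypertension.

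**Working it through.** **Inputs.** Write S for systolic and D for diastolic.

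- Normal (Interventions and Interactions): S ≤ 140 and D ≤ 90. The notation is taken to require both components; a looser reading would only widen the overlap.
- Mild alert by the subsection heading, with either component sufficient: S ≥ 140 or D ≥ 90.
- Mild alert by the first bullet read strictly: S > 140 or D > 90.

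**Step 1: where normal and the heading overlap.** Both hold exactly when (S = 140 and D ≤ 90) or (D = 90 and S ≤ 140). A reading such as 140/95 is not in the overlap, because it is not normal.

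**Step 2: six example readings.**

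| Reading | Normal message | Alert by heading | Alert by strict bullet |
|---|---|---|---|
| 139/89 | yes | no | no |
| 140/85 | yes | yes | no |
| 132/90 | yes | yes | no |
| 140/90 | yes | yes | no |
| 141/85 | no | yes | yes |
| 132/91 | no | yes | yes |

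The three middle boundary readings are called normal and also trigger the heading's alert.

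**Step 3: enumeration.** On integer readings with S from 80 to 220 and D from 40 to 140:

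- S = 140 with D from 40 to 90 gives 51 pairs.
- D = 90 with S from 80 to 140 gives 61 pairs.
- 140/90 is counted twice, so the overlap is 51 + 61 − 1 = 111 pairs.

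This count depends on the grid chosen. It confirms where the overlap lies and says nothing about how often it occurs. Normal against the strict bullet gives 0 overlapping pairs, but that reading contradicts the heading.

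**Step 4: what a boundary reading leads to.**

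- *140/85, new onset, no symptoms.* Under the heading: mildly elevated message, checklist, 10-minute recheck, MFM staff alerted within 4 hours, office visit in 1 to 3 days. Under the normal range: a normal message.
- *160/100, new onset, no symptoms.* Under the critical heading: MFM alert within 60 minutes and referral to OB triage. Under a strict reading of the critical bullet, only the mild pathway applies: 4 hours and an office visit in 1 to 3 days.

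**Step 5: the corrected rules.** With normal as S < 140 and D < 90, and alert as S ≥ 140 or D ≥ 90, each rule is the exact negation of the other. No reading meets both and none meets neither.

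**The case against.** The strongest reply is that the text largely settles the alert rule. The sentence after the normal range sends the reader to the definitions below, and the heading there is at or above 140/90. On that view the boundary woman does get the alert and the full pathway, and what remains is one wrong inequality sign on a reassurance message. The bullets can be read as saying only which components count, with the threshold taken from the heading above them. The same pattern in both subsections suggests loose wording, not a rival cut.

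Much of this is fair. The missed-alert consequence, and the whole of the 160/100 example, depend on the strict reading of the bullets, which is the less natural one. It is also true that:

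- the protocol is not the app's configuration record, so the app may already use one consistent cut;
- readings are repeated through Day 21, so a single boundary value is usually followed by others;
- for an asymptomatic woman with chronic or known hypertension, the mild pathway ends in continued monitoring, so less is at stake for her.

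None of this removes the overlap. If the heading governs, the app as described still calls the reading normal while alerting on it. If the bullet governs, the heading is wrong. The text is inconsistent either way.

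**Conclusion.** The point holds. As written, the normal range and the mild-elevation heading both claim any reading with systolic exactly 140 and diastolic at or below 90, or diastolic exactly 90 and systolic at or below 140. The at-or-above heading and above-threshold bullet also disagree at exactly 160 or 110, although no normal message is involved there.

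The severity is minor. The inconsistency is confined to boundary values and changes no sample size, endpoint or analysis figure. Confidence is high for the literal overlap between the normal range and the mild heading. Whether any woman would actually receive conflicting messages or miss an alert depends on the app's settings, which the documents do not give. Nor do they give a BP distribution, so no frequency is claimed. Nothing here concerns readings with both components below their cuts.

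**What to change.** - In Interventions and Interactions, define the normal range as systolic below 140 and diastolic below 90.
- In the first bullet of both alert subsections, say at or above the threshold, to match the headings.
- Confirm with the app vendor that the normal message and both alerts use these same cuts. The check is worth making because the protocol already reports that limits on customizing the app made its reminders differ from the intended schedule.

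The cost is a few words in three places and one settings check. No new data are needed and the analysis does not change.
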